5.0 THERAPEUTIC/DIAGNOSTIC AGENTS

Degarelix Drug Product

This is a commercially available, injectable, long acting analog of the native LHRH peptide. It is administered via subcutaneous injection to the abdominal region only. The manufacturer's instructions should be followed. Degarelix will be provided by Ferring Pharmaceuticals as Firmagon.

Radiation Therapy

Stereotactic, ultra-fractionated radiotherapy will be administered every other day for five total treatments using an intensity modulated treatment plan directing its dose of 8.0 Gy to the prostate and seminal vesicles. At least 3 days prior to CT simulation, 3 fiducial markers will be placed transrectally or transperineally within the prostate gland to be used for target localization on a daily basis for image-guided therapy. Treatment planning dose constraints will be optimized per criteria outlined in Section 9.0

Health-related Quality of Life Metrics

The Expanded Prostate Cancer Index Composite (EPIC) was developed at the University of Michigan and the University of California-Los Angeles. It was designed to assay health related quality of life among men with prostate cancer. EPIC has been validated in men with localized prostate cancer who underwent surgery, external beam radiation, or brachytherapy with or without adjuvant hormones. EPIC is both sensitive and specific to HR-QOL effects of these therapies and to HR-QOL effects of cancer progression. EPIC-26 was developed as a short-form version of the full EPIC and contains 26 items and the same 5 domains as the complete EPIC version (Urinary Incontinence, Urinary Irritative/Obstructive, Bowel, Sexual, and Hormonal). Information regarding the statistical validation of EPIC can be found at: <https://medicine.umich.edu/sites/default/files/content/downloads/Development%20and%20Validation%20of....pdf>

The Medical Outcomes Study SF-12 is a validated measure of General Health Function developed by RAND. It is intended to be used to derive 2 summary scores (physical and mental component summaries) relevant to general HR-QOL status. It provides a context for EPIC score results. The SF-12 items themselves are not included in the calculation of any EPIC domain scores.

The International Prostate Symptom Score (IPSS) index is a validated and widely used instrument that is currently administered as part of routine patient evaluation in our clinics. The IPSS index yields a single index score and represents a seven item questionnaire designed to assess urinary functioning, specifically urinary frequency, nocturia, weak urinary stream, hesitancy, intermittence, incomplete emptying, and urgency. Questions are rated on a six point Likert scale with higher scores indicating more difficulty in urinary functioning. This measure demonstrated a high internal consistency (Cronbach's alpha = 0.84) with excellent test-retest reliability ($r = 0.92$). The IPSS index also demonstrated good validity with strong associations with other measures of urinary difficulties. The IPSS index also showed appropriate sensitivity to change. This measure has been widely used in clinical practice and research protocols. We will be using the information obtained as a part of the standard of care visit for this research study.

6.0 CRITERIA FOR SUBJECT ELIGIBILITY

6.1 Subject Inclusion Criteria

- Biopsy proven intermediate risk prostate cancer, which includes patients with any one of the following variables:
 - Gleason 7 disease
 - PSA 10-20 ng/ml
 - Clinical T2b-T2c disease

Note: Patients who only have radiographic evidence of T3 disease (i.e. extracapsular extension, or seminal vesical invasion radiographically) will not be excluded.

- Serum testosterone \geq 240 ng/dL determined within 2 months prior to enrollment
- At least 4 weeks must have elapsed from major surgery
- KPS \geq 80%
- Prostate size as determined on MRI to be $<$ 90 cc. Prostate size can be determined on CT scan if MRI is not available.
- 18 years of age or older
- IPSS \leq 20
- Patient must be available for follow-up. After 2 years of follow-up following post-treatment biopsy, telephone-based follow-up will be acceptable
- Laboratory test findings within 8 weeks of randomization:
 - Adequate hepatic function with serum bilirubin \leq 1.5 times the upper institutional limits of normal (ULN), ALT and AST \leq 2.5 x ULN. Patients with a history of Gilbert's syndrome may be enrolled if the total bilirubin is $<$ 3 mg/dL with a predominance of indirect bilirubin
 - Adequate renal function with serum creatinine \leq 1.5 x ULN
 - Adequate hematologic function with absolute neutrophil counts \geq 1,500 cell/mm³ and platelets \geq 100,000 cells/mm³ and hemoglobin value \geq 9 g/dL (Note: patients whose anemia has been corrected to a hemoglobin value \geq 9 g/dL with blood transfusions are allowed)

6.2 Subject Exclusion Criteria

- CT or MRI evidence of metastatic disease to the bone.
- Patients with one or more positive lymph nodes considered suspicious as determined by clinical assessment on MRI or CT
- Prior treatment for prostate cancer, including history of chemotherapy, hormonal therapy within 30 days of enrollment or surgery for prostate cancer (except for prior TURP or greenlight PVP which would be allowed)
- History of another malignancy within the previous 3 years except for the following: adequately treated basal cell or squamous cell skin cancer, superficial bladder cancer, currently in complete remission, or any other cancer that has been in complete remission for at least 3 years
- Patients with Crohn's disease or ulcerative colitis

7.0 RECRUITMENT PLAN

Potential research subjects will be identified by a member of the patient's treatment team, the protocol investigator, or the research team at Memorial Sloan-Kettering Cancer Center (MSK). If the investigator is a member of the treatment team, s/he will screen their patient's medical records for suitable research study participants and discuss the study and their potential for enrolling in the research study. Potential subjects contacted by their treating physician will be referred to the investigator/research staff of the study.

The principal investigator may also screen the medical records of patients with whom they do not have a treatment relationship for the limited purpose of identifying patients who would be eligible to enroll in the study and to record appropriate contact information in order to approach these patients regarding the possibility of enrolling in the study.

During the initial conversation between the investigator/research staff and the patient, the patient may be asked to provide certain health information that is necessary to the recruitment and enrollment process. The investigator/research staff may also review portions of their medical records in order to further assess eligibility. They will use the information provided by the patient and/or medical record to confirm that the patient is eligible and to contact the patient regarding study enrollment. If the patient turns out to be ineligible for the research study, the research staff will destroy all information collected on the patient during the initial conversation and medical records review, except for any information that must be maintained for screening log purposes.

In most cases, the initial contact with the prospective subject will be conducted either by the treatment team, investigator or the research staff working in consultation with the treatment team. The recruitment process outlined presents no more than minimal risk to the privacy of the patients who are screened and minimal PHI will be maintained as part of a screening log. For these reasons, we seek a (partial) limited waiver of authorization for the purposes of (1) reviewing medical records to identify potential research subjects and obtain information relevant to the enrollment process; (2) conversing with patients regarding possible enrollment; (3) handling of PHI contained within those records and provided by the potential subjects; and (4) maintaining information in a screening log of patients approached (if applicable).

In regards to accrual numbers, MSK plans to enroll 50 patients per year at Main Campus, and 50 patients per year between all regional sites.

This limited waiver will apply only to MSKCC.

8.0 PRETREATMENT EVALUATION

The following must be completed prior to randomization:

- MSKCC pathology review confirming cancer
- The following screening tests and assessments should be performed within 8 weeks prior to randomization to confirm eligibility:
 - Full medical history and physical exam, including DRE and performance status
 - MRI of the prostate and pelvis within 6 months of randomization. (CT of the pelvis with contrast may be performed if MRI is contraindicated)
 - Radionuclide bone scan if there is suspicion of bone metastases within 6 months of randomization.
 - Lab tests:
 - PSA
 - Baseline CBC, CMP (Na, K, Cl, CO₂, Ca, T. Protein, Albumen, Creatinine, Glucose, BUN, Alk Phos, ALT, AST, T. Bili), Conj. Bili,

- Testosterone level
- Questionnaires:
 - IPSS documenting score < 20
 - EPIC
 - SF-12

Once eligibility is confirmed, the patient should undergo randomization.

9.0 TREATMENT/INTERVENTION PLAN

Androgen Deprivation Therapy Arm: Within two weeks prior to the first injection, patients will obtain routine blood tests including CBC and liver function tests and testosterone levels. Degarelix injections will be administered in the radiation oncology clinics monthly. The first injection is administered as a boost, 240 mg given as two subcutaneous injections of 120 mg at a concentration of 40 mg/mL which is then followed by 80 mg given as one subcutaneous injection at a concentration of 20 mg/mL every 28 days (+/- 7days). In 10% of patients a skin rash could develop at the injection site. If this is noted and symptomatic for the patient the injection could be switched to monthly Lupron intramuscular injections (7.5.mg).

Study treatment: Stereotactic, Ultra-Fractionated Radiotherapy (same for each arm)

Intensity-modulated, image-guided, ultra-hypofractionated external beam radiotherapy will incorporate prostate and seminal vesicles and this planning target volume will receive 8 Gy x 5 fractions. As per routine for intermediate risk patients, the lymph nodes will not be included within the treatment portal.

9.1 Prior to Simulation

Fiducial markers as per routine will be placed into the prostate to be used for image guidance and this will be performed a minimum of 3 days prior to simulation.

9.2 Simulation

- Patients will perform a bowel preparation the night before simulation.
- Patients will be supine and positioned in a thermoplastic mold with Aquaplast immobilizations routinely done.
- Oral contrast may be administered for simulation.
- A Foley catheter will be placed for simulation only.
- A rectal catheter will be placed for simulation only.
- CT images will be obtained as per existing department protocols and sent to the treatment planning system
- If MR images will be obtained as per existing department protocols they will be sent to the treatment planning system as well.

Participating sites may follow institutional simulation guidelines as long as the simulation guidelines have been reviewed and approved by the PI.

9.3 Treatment Planning

- CTV will include the prostate, seminal vesicles, and any areas at risk of extra-capsular extension.

- PTV will include a 5 mm expansions on CTV in all directions save for posterior; the posterior expansion will be 3 mm.
- The following normal tissue should be contoured: bladder, rectum (The rectum should be contoured from the anus to the rectosigmoid flexure), urethra, penile bulb, bilateral femoral heads and necks, large bowel, small bowel, external body contour. For PTV, the D95% should be \geq 90% of the prescribed dose of 8 Gy per fraction.

Constraints to Normal Tissue

Rectum:

- 1) Maximum dose \leq 41.2 Gy
- 2) Dose to 1cc \leq 38.5 Gy ($D_{1cc} \leq 38.5$ Gy)
- 3) $V_{24Gy} \leq 25\%$
- 4) Mean dose \leq 16.4 Gy
- 5) $V_{30.15Gy} \leq 8CC$

Urethra:

- 1) Maximum dose \leq 42 Gy
- 2) Dose to 1cc \leq 40 Gy ($D_{1cc} \leq 40$ Gy)

Bladder:

- 1) Maximum dose \leq 42 Gy
- 2) $V_{36Gy} \leq 10\%$
- 3) $V_{20Gy} \leq 50\%$

Large Bowel:

- 1) Maximum dose \leq 29 Gy

Small Bowel:

- 1) Maximum dose \leq 25 Gy

Femoral Heads:

- 1) Maximum dose \leq 31 Gy
- 2) $V_{21.6Gy} \leq 10 CC$

Penile Bulb

- 1) Maximum dose \leq 40 Gy
- 2) $D_{3CC} \leq 21.6Gy$

- Beam arrangements, optimization structures and optimization parameters will be defined at the discretion of the treatment planner using routine departmental procedures.
- The treatment plan will be approved and reviewed by the attending physician.
- The treatment plan will go through quality assurance procedures per departmental guidelines.
- Treatment should be initiated approximately 14 days after simulation (+/-7 days).

9.4 SBRT Delivery

- Patients will be treated every other day.
- Metamucil 1 teaspoon in 8 ounces of water should be taken prior to simulation and continued on a daily basis and continue until completion of radiation treatment. In addition a fleets enema 1-3 hours before simulation and each treatment will also be advised for the patient to take.
- Patients will be encouraged to evacuate their bowels approximately 1 hour prior to treatment.
- Patients will be immobilized as in simulation and aligned using lasers and skin tattoos/marks in treatment room.
- Any necessary translational shifts in patient position will be made once based on position of fiducial markers have been spatially reconciled with the simulation reference data set.
- Any deviation of $\geq 2\text{mm}$ from the planned position will require treatment interruption and positional correction.
- Participating sites may follow institutional guidelines for treatment targeting, as long as treatment targeting methods have been reviewed and approved by the PI.

10.0 EVALUATION DURING TREATMENT/INTERVENTION

10.1 Evaluation during Treatment

- Patient completion of study specific PRO assessments
 - EPIC-26
 - SF-12
 - IPSS

10.2 Evaluation during Follow-Up

- Physical exam
- Performance status
- Clinical evaluation for late urinary, rectal toxicity and sexual dysfunction per standard CTCAE assessments and grading.
- PSA
- Serum Testosterone
- EPIC – 26
- SF-12
- IPSS
- Prostate biopsy, 24-30 months post SBRT

Table 1. Schedule of assessments

	Pre-Treatment	During Radiation Therapy	Follow up
	Within 8 weeks prior to study randomization	Within 2 week prior to the initiation of Degarelix ¹	
Informed consent	X		
Medical history	X		
Physical exam	X		X
Digital rectal exam	X		
Performance status	X		X
Histologic or pathologic confirmation of disease	X ²		
MRI prostate/pelvis within 6 months of randomization	X ³		
Bone scan within 6 months of randomization if determined necessary	X		
EPIC-26	X	X ⁴	X
SF-12	X	X ⁴	X
IPSS	X	X ⁴	X
PSA	X	X	X
CBC	X	X	
Comp	X	X	
Liver function tests	X	X	
Serum testosterone	X	X	X
Toxicity assessment			X
Degarelix		X ⁵	
Fiducial marker placement		X ⁶	
Radiation therapy		X'	
Biopsy			X ⁸

1. For patients randomized to the ADT + SBRT arm
2. Histologic or pathologic confirmation of disease can be done anytime prior to randomization.
3. CT of the pelvis with contrast may be performed if MRI is contraindicated.
4. To be completed during treatment, at the 3rd of 5th fraction of later
5. Degarelix will be given monthly (+/- 7 days), 3 months before and 3 months after radiation therapy.
6. Fiducial markers will be placed 3 days before simulation.
7. Radiation therapy will be given every other day.
8. Prostate post-treatment biopsy will be performed once at 24-30 months post SBRT.

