1.0 PROTOCOL SUMMARY AND/OR SCHEMA

For this proposed Phase III study, intermediate risk prostate cancer patients will be randomized to receive 6 months of Androgen Deprivation Therapy (ADT) in conjunction with stereotactic body radiosurgery (SBRT) directed to the prostate versus SBRT alone. The patient population eligible will include patients with NCCN defined intermediate risk disease. ADT will be administered with Degarelix monthly injections. SBRT will be delivered with a prescription dose of 8 Gy x 5 to the planning target volume. Inter-fraction motion targeting and target position corrections will be utilized for each of the 5 treatment fractions. All patients will be followed every 6 months for 2 years and will undergo routine 24-30 months post-SBRT prostate biopsies to assess for local tumor control.

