2.0 OBJECTIVES AND SCIENTIFIC AIMS

Primary Objectives

- To compare 24-30 month post-SBRT prostate 12 core biopsy outcomes between intermediate risk patients treated with SBRT and short course ADT versus SBRT alone.

Secondary Objectives

- To assess whether the addition of 6 months of ADT with high dose SBRT decreases incident rates of biochemical failure and distant failure, or improves survival rate for intermediate risk prostate cancer patients compared to SBRT alone.
- To assess the differences in short-term and long-term quality of life outcomes by comparing EPIC-26, IPSS, and SF-12 survey results between intermediate risk prostate cancer patients treated with SBRT + short course ADT versus SBRT alone.

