4.0 OVERVIEW OF STUDY DESIGN/INTERVENTION

4.1 Design

For this proposed Phase III study, intermediate risk patients will be randomized to received 6 months of ADT which would be given 3 months prior to planned SBRT to the prostate and 3 months during/following SBRT. ADT will be administered via Degarelix monthly injections. SBRT will be delivered with a prescription dose of 8 Gy x 5 prescribed to the planning target volume. Inter-fraction motion targeting and target position correction will be utilized as is routine in our department during the treatment SBRT.

The primary end-point of this study is the proportion of patients who have positive 2-year post-treatment prostate biopsies. Based on our previous published experience, we expect that the 2-year rate of a positive biopsy using ADT with ultra-hypofractionated SBRT for intermediate risk features would be 15% compared to 35% for those patients treated with SBRT alone. We anticipate we would require powering the study with 100 patients in each arm. Randomization will be stratified by favorable-intermediate and unfavorable-intermediate risk status (unfavorable-intermediate risk will be defined as patients having Gleason 4+3, >50% positive biopsy cores or 2 intermediate risk factors combined such as Gleason 7 and PSA > 10 ng/ml).

The primary endpoint is the 2-year biopsy which is generally scheduled at the end of the second year. However, we have provided some flexibility as to prevent prospective and retrospective deviations. Therefore, we have chosen to allow the primary endpoint biopsy to occur between 24-30 months which we believe is reasonable based on our clinical experience.

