4.2 Intervention

Eligible patients with intermediate risk disease will be randomized to ADT with SBRT versus SBRT alone. The ADT patients will be treated with monthly degarelix injections. After three months (+/- 1 month) have elapsed, these patients as per routine would undergo fiducial marker placement followed by simulation and SBRT to follow. For this cohort ADT will continue until 6 months of Degarelix is administered. If a patient develops an allergic reaction to the Degarelix injection, he may be switched to Leuprolide acetate monthly injections in its place.

For patients treated with SBRT alone referral will be made for fiducial marker placement with simulation and SBRT to follow. Patients will then be followed at 6 month intervals with routine serum PSA and testosterone testing. All patients will undergo a post-SBRT standard 12 core prostate biopsy at 24-30 months after completion of SBRT to evaluate local tumor control status.

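### Short-term quality of life is an objective, but on the natural reading of the schedule no survey falls in the first 6 months after SBRT, the period in which ADT ends

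*Combined protocol and SAP*

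**What the plan says.** Section 2.0 sets as a secondary objective "To assess the differences in short-term and long-term quality of life outcomes by comparing EPIC-26, IPSS, and SF-12 survey results" between the two arms.

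The survey times come from several places:

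- **Baseline.** Section 8.0 lists the questionnaires among the screening assessments, and Table 1 puts them "Within 8 weeks prior to study randomization".
- **On treatment.** One set during SBRT. Footnote 4 to Table 1 reads "To be completed during treatment, at the 3rd of 5th fraction of later", which I take to mean the third of the five fractions or later.
- **Follow-up.** Section 10.2 and Table 1 list all three instruments under follow-up without dates. The only interval is in Section 1.0, "All patients will be followed every 6 months for 2 years", and Section 4.2, "Patients will then be followed at 6 month intervals with routine serum PSA and testosterone testing".

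ADT is planned to continue past SBRT. Section 4.1 describes six months of ADT "which would be given 3 months prior to planned SBRT to the prostate and 3 months during/following SBRT", and footnote 5 to Table 1 says "Degarelix will be given monthly (+/- 7 days), 3 months before and 3 months after radiation therapy". Section 14 names no survey times. It compares the arms by Wilcoxon rank sum tests whenever the surveys happen to be given.

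**The concern.** Section 3.3 gives the quality-of-life cost of ADT as a reason why high-dose SBRT might be used without it. Quality of life is therefore one side of the decision this trial is meant to inform.

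The only scheduled survey between baseline and the first follow-up visit is the on-treatment one. At that point an SBRT-alone patient may have had only two or three fractions, so the answers say little about symptoms that follow SBRT. An ADT patient is part-way through the drug. If nothing more is collected until 6 months after SBRT, the trial has no survey at full ADT exposure and none in the early period after SBRT, in either arm. It then cannot show whether ADT adds to early post-SBRT symptoms. Patient-reported data not collected in that window cannot be recovered later.

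No other scheduled measure fills the gap. Section 10.2 places toxicity grading at follow-up and describes it as late toxicity, and Section 11 counts urinary or rectal toxicity as an adverse event only from grade 3.

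**Working it through.** The plan gives no figure for this gap, so there is none to reproduce. I built a timeline with day 0 as the first degarelix injection and 1 month = 30.4375 days.

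**Inputs**
- Lead-in before fiducials, simulation and SBRT: 3 months, plus or minus 1 (Section 4.2).
- Planning lag: either 0 (the lead-in runs up to SBRT itself), or 3 days from fiducials to simulation (Section 9.1) plus 14 days, plus or minus 7, to SBRT (Section 9.3). This gives 10, 17 or 24 days.
- SBRT: five fractions every other day (Section 9.4), so fraction 3 is at start + 4 days and fraction 5 at start + 8 days.
- ADT length: 6 × 28 = 168 days (interval in Section 9.0), or 6 calendar months = 183 days. The number of injections is not stated, so six is an assumption.
- First follow-up survey: 6 months (183 days) after the end of SBRT. This anchor is inferred.

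**Formulas**
- SBRT end = lead-in + lag + 8.
- ADT end relative to SBRT = ADT length − SBRT end.
- First survey relative to ADT end = SBRT end + 183 − ADT length.

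Example, planned lead-in with lag and 168 days of ADT: SBRT end = 91 + 17 + 8 = day 116; ADT ends 168 − 116 = 52 days (1.7 months) after SBRT; first survey at 116 + 183 = day 299, which is 299 − 168 = 131 days (4.3 months) after ADT ends.

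| Lead-in | Lag (days) | Fraction 3 (day) | SBRT end (day) | ADT ends after SBRT, months (168 d / 6 mo) | First survey after ADT ends, months (168 d / 6 mo) |
|---|---|---|---|---|---|
| 2 mo | 0 | 65 | 69 | 3.3 / 3.7 | 2.7 / 2.3 |
| 2 mo | 10 | 75 | 79 | 2.9 / 3.4 | 3.1 / 2.6 |
| 3 mo | 0 | 95 | 99 | 2.3 / 2.7 | 3.7 / 3.3 |
| 3 mo | 17 | 112 | 116 | 1.7 / 2.2 | 4.3 / 3.8 |
| 4 mo | 0 | 126 | 130 | 1.3 / 1.7 | 4.7 / 4.3 |
| 4 mo | 24 | 150 | 154 | 0.5 / 0.9 | 5.5 / 5.1 |

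In every row ADT ends after the on-treatment survey and before the first follow-up survey. I did not vary the 7-day injection window. A single 7-day shift of the end of ADT does not change this order: the smallest margin after SBRT becomes 14 − 7 = 7 days.

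**Length of the gap.** From fraction 3 it is 4 + 183 = 187 days (6.1 months); from fraction 5 it is 6.0 months. The freedom to survey later in the course changes it by only 4 days.

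**Exposure at the on-treatment survey.** On the planned lead-in, fraction 3 is on day 95 to 112, or 3.1 to 3.7 months into ADT. That is 95/183 = 52% to 112/168 = 67% of the planned exposure.

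**Other anchor.** If follow-up were counted from the first injection, the first ADT-arm survey would be on day 183, within 183 − 168 = 15 days of the end of ADT. If SBRT-alone patients were counted from the start of SBRT, their first survey would be 183 − 8 = 175 days (5.7 months) after SBRT ends. They would still have none in the early months.

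**The case against.** The strongest reply is that the schedule is adequate for a secondary endpoint. The protocol does not define short-term, and an on-treatment survey plus one at 6 months could serve. Lining surveys up with SBRT rather than randomization is a reasonable choice when one arm has a 3-month lead-in. The primary biopsy endpoint is untouched. All of this stands, and it limits the weight of the point.

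Three stronger readings are tempting, and the documents do not support them.

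- **That the end of ADT is certainly never measured.** The 6-month anchor is inferred. The sentence in Section 4.2 follows the SBRT instructions and opens with a word of sequence, but it names PSA and testosterone, not surveys. Section 1.0 gives no starting point, and Section 12 starts the outcome clocks at the beginning of treatment. Counted from the first injection, an ADT-arm survey would fall near the end of ADT.
- **That ADT effects will already be reversing at the first follow-up survey.** Section 11 places reversal 6 to 12 months after ADT stops. The survey comes 2.3 to 5.5 months after, so effects should still be detectable.
- **That the comparison would therefore understate the burden of ADT.** Two surveys fall while effects are expected. Underestimation is possible but not shown.

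IPSS is also part of routine clinic evaluation (Section 5.0), and injections are given in the radiation oncology clinics (Section 9.0), so some unscheduled IPSS values may exist for ADT patients. They would cover only urinary symptoms, not the bowel, sexual or hormonal domains of EPIC-26.

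**Conclusion.** The point holds as a cheap improvement to a secondary objective, not as an error affecting the primary result. With follow-up counted from SBRT, both arms have no survey for about 6 months after SBRT. ADT ends inside that gap, 0.5 to 3.7 months after SBRT across the lead-in and planning windows (1.7 to 2.7 on the planned lead-in). The first follow-up survey comes 2.3 to 5.5 months after ADT ends (3.3 to 4.3 on the planned lead-in). With follow-up counted from the first injection, the ADT-arm part of the gap largely closes but the early post-SBRT gap in the SBRT-alone arm remains. The lack of a stated anchor is therefore itself worth correcting.

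The conclusion assumes six months of ADT, taken as 168 or 183 days, and that no follow-up survey date is given beyond the 6-month interval. The header of Table 1 is broken in the text copy, but the argument rests on footnote 4 and Sections 1.0 and 4.2, not on column alignment.

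**What to change.** In Table 1, state that follow-up survey times count from the end of SBRT in both arms. Add one EPIC-26, SF-12 and IPSS set at 3 months after the end of SBRT, with the same window in both arms, completed remotely if no visit is due. In Section 14, name it as the short-term quality-of-life time point and keep the on-treatment survey as descriptive.

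Do not tie the new survey to the last injection visit. With six injections 28 days apart, the last is on day 5 × 28 = 140. On the planned lead-in with lag that is 140 − 116 = 24 days, about 3 weeks, after SBRT. Surveying ADT patients then and SBRT-alone patients at 3 months would misalign the arms and still precede full exposure. At 3 months, the survey falls 3 − 2.7 = 0.3 to 3 − 1.7 = 1.3 months after ADT ends on the planned lead-in, before the reversal period in Section 11.

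The cost is one more short questionnaire set for about 223 patients, some tracking effort by existing study staff, and some non-response. No procedure or treatment changes, and the primary endpoint is unaffected.
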